## STUDY DESIGN

This is a Phase II, open-label, prospective pilot study of APL-2 conducted in subjects with a primary diagnosis of wAIHA or CAD in parallel. The study will consist of up to 24 subjects, up to 12 subjects with a primary diagnosis of wAIHA in Cohort 1 and up to 12 subjects with a primary diagnosis of CAD in Cohort 2. Subjects in each cohort will be randomly (1:1) assigned to receive either 270 mg/d or 360 mg/d of APL-2 treatment for up to 12 months (Part A, the Core Study Phase).

Following Day 336 and the completion of the Part A Core Study Phase, subjects will be eligible to participate in Part B, a Long-term Extension Phase, in order to continue to receive treatment with APL-2. The Long-Term Extension Phase is described in Section 17.3.1.

Through Part A (Day 336), dose escalation from 270 mg/d to 360 mg/d, or de-escalation from 360 mg/d to 270 mg/d may occur after thorough evaluation of available safety and laboratory assessment.

Safety will be assessed throughout the study; serial blood and urine samples will be collected for these assessments. Blood samples will be collected for the assessment of APL-2 PK. Additional samples for assessment of PD will also be collected.

Screening will take place within 30 days prior to the start of dosing on Day 1. If needed (see inclusion criteria), *Neisseria meningitides* types A, C, W, Y and B (administered as two separate vaccines), PCV13 or PPSV23, and Hib vaccinations will be administered prior to dosing on Day 1.

Subjects who meet all the inclusion criteria and none of the exclusion criteria will be enrolled into the study on Day 1 at a time designated by the PI. During study, the first 3 daily SC doses of APL-2 (Day 1 to 3) as well as doses on Day 7 and 14 will be administered at the clinical site. From Day 4 to Day 336 daily doses of APL-2 will be administered off-site by a study nurse or self-administered by the subject and/or caregiver, at the subject's home, workplace, or other location convenient to the subject with the exception of those days where dosing is at the clinical site. At any time during the study, if subjects discontinue treatment, or if after the conclusion of the Part A Core Study Phase a subject does not elect to enter the Part B Long-Term Extension Phase, subjects will return to the clinical site for safety follow-up study procedures after 6 weeks, followed by final study procedures at an Exit Visit after another 6 weeks. See Study Flowchart in Section 3.

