## 12.7 Dose Escalation or De-escalation and Periodic Safety Review

Through the Part A Core Study Phase (up to Day 336), dose escalation will never exceed 360 mg/d without approval from the SMC and the IRB. Decisions to dose escalation or de-escalation

between the two dose groups may be made by the Sponsor. Review of doses above 360 mg/d will be comprised of SMC and IRB approval examination of all cumulative safety, tolerability and efficacy data (e.g., physical examinations, ECGs, vital signs, clinical laboratory tests, and adverse events) and a thorough assessment of all safety data will occur prior to initiation. PK/PD data and predicted exposure for subsequent doses based on emerging PK data will also be reviewed prior to determining the proposed dose adjustment.

The same review process will be followed if any additional cohorts are added to the study.

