### 3.3 Study Design

This is a Phase II, open-label, prospective pilot study of APL-2 conducted in subjects with a primary diagnosis of wAIHA or CAD in parallel. The study will consist of up to 24 subjects, a target of 12 subjects with a primary diagnosis of wAIHA in Cohort 1 and a target of 12 subjects with a primary diagnosis of CAD in Cohort 2. Subjects will be randomized 1:1 to a 270mg or 360mg daily SC APL-2 dosage group within each cohort for up to 12 months (Part A, the Core Study Phase).

Following Day 336 and the completion of the Part A Core Study Phase, subjects will be eligible to participate in Part B, a Long-Term Extension Phase, in order to continue to receive treatment with APL-2. The Long-Term Extension Phase is described later in this section.

Through Part A (Day 336), dose escalation from 270 mg/d to 360 mg/d, or deescalation from 360 mg/d to 270 mg/d may occur after a thorough evaluation of available safety and laboratory assessment.

Safety will be assessed throughout the study; serial blood and urine samples will be collected for these assessments. Blood samples will be collected for the assessment of APL-2 PK. Additional samples for assessment of PD will also be collected.

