## 5. STATISTICAL ANALYSIS METHODOLOGY

In general, tables will be presented by randomized dose level within cohort (270 mg vs. 360 mg) and by cohort.

Tabulations for continuous data will use a standard set of descriptive statistics: number of observations available (n), mean, standard deviation (SD), median, and range (minimum, maximum).

Categorical or dichotomous data will be tabulated using frequencies (counts and percentages). The numerator and denominator for each percentage calculation will be specified in the footnotes of table shells.

Data listings will present all information recorded in eCRFs for all subjects and visits. All listings will be sorted by cohort and subject number.

Unless otherwise noted, tabulations or descriptive statistics by visit during the Part A Core Study Phase will include only scheduled visits through Visit 15 (i.e. summary statistics will not include follow-up Visits 16 and 17.

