#### Version 1.0

Compliance =

number of complete study doses administered prior to study discontinuation total number of expected study doses prior to study discontinuation x 100

> Compliance during Part A, Part B, and total on-study time will be listed by subject. Additionally, exposure and compliance will be summarized for Part A, Part B, and total time on study using descriptive statistics by randomized dose level and by cohort.

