## Adverse Events Summary

An AE data listing of all AEs collected on study, including verbatim term, preferred term, treatment, severity, and relationship to treatment will be provided. Serious Adverse Events (SAEs), adverse events of special interest, and details of subjects withdrawing due to adverse events will also be listed. The start day (relative to the first dosing day), and the duration of AEs will be included in listings.

A topline summary for Part A, Part B, and Overall will present the number of events and the number of subjects by randomized dose level and by cohort with:

- any TEAE
- any TEAE considered as related to study drug (evaluated by the investigator as Unlikely Related, Unrelated, Possibly Related, Probably Related, Definitely Related, or Unknown)
- any serious TEAE
- Maximum severity TEAE of mild, moderate, severe, life threatening, and death; i.e. a subject with TEAEs at different intensities will be summarized at the most severe intensity
- any TEAE of special interest
- any TEAE leading to study drug discontinuation
- any TEAE leading to death

The table will also include the total number of TEAEs reported in each cohort and overall. The total number of unique terms within subjects will also be presented, counting each TEAE only once within each subject.

Additionally, the following will be tabulated with the number of events and the number/percent of subjects by randomized dose level in each cohort, and by cohort. Summaries will be ordered by descending order of event count in the overall column. All summary tables will be presented by study part and over the whole study, where AEs will be categorized by the Part in which the AE started i.e. an AE which began during the Part A Core Study Phase will be categorized under Part A even if it continues into Part B (unless it increases in severity).

- TEAEs by SOC and preferred term
- TEAEs by preferred term

• TEAEs regarded as at least possibly related to study drug by SOC and preferred term

The following will also be tabulated with the number/percent of subjects by randomized dose level in each cohort and by cohort:

- TEAEs and Serious AEs by SOC, preferred term, and maximum severity
- TE AESIs by SOC, preferred term, and maximum severity if applicable
- TE AESIs (regarded as at least possibly related to study drug) by SOC, preferred term, and maximum severity

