#### 5.4 Pharmacokinetic Analysis

All summaries and analyses of the pharmacokinetic data will be based on the Pharmacokinetic Set.

APL-2 concentrations reported as below the limit of quantification (BLQ) will be taken as zero for linear plots, and equal to the lower limit of quantification (LLOQ) for semi-logarithmic plots. For the computation of descriptive statistics, BLQ will be taken as zero, except for the calculation of the geometric mean where the LLOQ will be used.

A listing of all APL-2 concentrations will be presented by dose. The actual study time will be listed, along with the deviation and percent deviation from nominal time.

APL-2 concentrations will be summarized by planned study visit using descriptive statistics by randomized dose group, actual dose at the time of the visit. That is, at each visit, the descriptive statistics will be presented for:

- · All randomized 270mg dose group, regardless of current dose
- · All randomized 360mg dose group, regardless of current dose
- Subjects randomized to 270mg and on 270mg dose at time of visit
- Subjects randomized to 360mg and on 360mg dose at time of visit

If a subject discontinues APL-2 dosing, then concentrations from samples collected more than 1 day after the last dose will be excluded from calculations.

The number of subjects with a value > BLQ will also be tabulated.

Linear and log-linear ( $\pm$  SE) concentration profile plots against time will be produced for each dose group.

Subjects that changed doses at any point during the study will have individual APL-2 concentration plots against time presented by study day, with APL-2 dose by study day visible on the upper portion of the plot.

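### Part A adverse-event and exposure tables are by randomised dose and cohort only; if subjects change dose, no visible table shows events or time by dose received

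*SAP*

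**What the plan says.** The Part A SAP (version 1.0, 27 Apr 2020) sets its table columns in section 5: "In general, tables will be presented by randomized dose level within cohort (270 mg vs. 360 mg) and by cohort". Section 5.2.1 follows that rule for the topline TEAE table, the tables by system organ class and preferred term, and the SAE and AESI tables by maximum severity; for example, TEAE summaries "will be tabulated with the number of events and the number/percent of subjects by randomized dose level in each cohort". Under section 5.1.5, exposure and compliance are "summarized for Part A, Part B, and total time on study using descriptive statistics by randomized dose level and by cohort".

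Dose changes are permitted in both directions during Part A. Protocol section 9 says they "may occur after thorough evaluation of available safety and laboratory assessment", and SAP section 3.3 repeats this. Protocol section 12.7 says decisions on moves "between the two dose groups may be made by the Sponsor". Protocol section 11.3.4 also lets further dose levels be added, up to 360 mg/d.

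The SAP expects subjects to receive both doses. Section 5.4 states: "Subjects that changed doses at any point during the study will have individual APL-2 concentration plots against time presented by study day", with the dose drawn above the profile. It derives Ctrough,max separately at each dose for such subjects. The concentration tables add rows such as "Subjects randomized to 270mg and on 270mg dose at time of visit".

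The AE listing has a treatment column, but the SAP does not say whether this is the randomised dose or the dose at onset.

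**The concern.** Incidence and severity of TEAEs is the primary endpoint. Protocol section 7.2.1 gives support for identifying a dose as a reason for including two. If a subject moves from one dose to the other, every event starting afterwards is counted under a dose that the subject is no longer taking. The time on the new dose is credited to the old column too.

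The final-analysis SAP (08 Nov 2022) does not fill the gap. Its Safety Set keeps only subjects who roll over and take 1,080 mg (section 4.1), and its AE and exposure tables are by cohort and study part, with no 270/360 split (sections 5.1.6.3 and 5.2.1.6). The Part A report is therefore the only visible place where adverse events are split by daily dose.

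The stake is limited. Amendment 4 had already set the planned Part B regimen (Protocol section 7.2.2), and neither SAP applies formal inference. What is at issue is description: a reader of the Part A tables could not see which events began on which dose, or how long subjects spent on each.

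**Working it through.** **Text check.** Displays in the Part A SAP, by the dose they use:

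| Display | Dose used |
|---|---|
| TEAE, SAE and AESI tables (5.2.1) | Randomised |
| Exposure and compliance tables (5.1.5) | Randomised |
| Concentration tables (5.4) | Randomised, plus rows for subjects still on their randomised dose |
| Ctrough,max (5.4) | Received |
| Individual PK plots for switchers (5.4) | Received, by study day |
| Dosing listing (5.1.5) | Received, by subject |
| AE listing (5.2.1) | Not defined |

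The extra concentration rows leave out a switcher once on the new dose. No visible table links adverse events to dose received.

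**Illustration.** The plan has no figure of its own to reproduce, and the documents give no number or timing of switches.

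From the documents: up to 6 subjects per dose within a cohort (Protocol synopsis) and 336 days of dosing (Protocol 11.3.2). Assumed: everyone completes; constant event rates; 20% risk over 336 days on 270 mg; true 360:270 rate ratio R of 2 or 1.5; one subject escalates at Day 84.

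- Expected events per subject over 336 days on 270 mg: -ln(0.8) = 0.2231.
- 270 column without switching: 6 × 0.2231 = 1.34.
- 360 column: R × 1.34.
- 270 column with one escalator: 5 × 0.2231 + 0.2231 × 84/336 + R × 0.2231 × 252/336.
- The last term is the part that starts on 360 mg.
- SE of the log rate ratio without switching (Poisson): sqrt(1/270 events + 1/360 events).

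| | R = 2 | R = 1.5 |
|---|---|---|
| 360 column, events | 2.68 | 2.01 |
| 270 column with one escalator | 1.51 | 1.42 |
| of which started on 360 mg | 0.33 | 0.25 |
| Share of the column | 22% | 18% |
| Apparent rate ratio | 2.68/1.51 = 1.78 | 2.01/1.42 = 1.41 |
| SE of log rate ratio | 1.06 | 1.12 |
| Shift in log ratio | ln(2/1.78) = 0.12 | ln(1.5/1.41) = 0.06 |
| Shift as share of one SE | 11% | 5% |

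With two Day 84 escalators the shares are 40% and 33%, and the apparent ratios 1.60 and 1.33.

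Percent of subjects moves less. At R = 2 with one escalator, the 270 column goes from 20.0% to 22.1% against 36.0%, so the gap falls from 16.0 to 13.9 points. The SE of that gap is sqrt(0.2 × 0.8/6 + 0.36 × 0.64/6) = 25.5 points.

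Subject-time with one escalator, by dose received: 270 mg (5 × 336 + 84)/365.25 = 4.83 years; 360 mg (6 × 336 + 252)/365.25 = 6.21 years. By randomised dose, both are 6 × 336/365.25 = 5.52 years.

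**The case against.** The strongest reply is that nothing here is an error. The columns are labelled as randomised dose, they preserve the 1:1 allocation, and they deliver the tabulation by cohort and dose group that Protocol section 15.2.2.1 asks for. The analysis is descriptive, and subgroup analyses are declined because numbers are small. The SAP's list of planned outputs is not in the copy reviewed, so a by-dose-received table may exist there. Time on dose is already drawn for every switcher in the PK plots, and AE start day and dosing are both listed; with up to 6 subjects per cell, a reader can match them. A table by dose at onset would not be a randomised comparison: switches follow safety and laboratory review, time after a switch is always later study time, and early events may reflect the previous dose.

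Most of this stands. It limits the point to a supplementary display and rules out replacing the planned tables. It does not close the gap. The plots show dose but not adverse events, the listings leave the linking to the reader, and the AE listing's treatment column is undefined.

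A reader might infer more: that the randomised-dose tables are wrong, that events cannot be traced to dose, or that the dose comparison is materially biased. The documents do not support these readings. The tables are what they claim to be, reconstruction from listings is possible, no switch is documented, and the illustrated shifts are a small fraction of the sampling error.

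**Conclusion.** The point holds as a minor omission in the visible text. If subjects change dose in Part A, post-switch events are tabulated only under the randomised dose, and no visible table gives adverse events or subject-time by dose received. By-cohort totals are unaffected, and with no switchers nothing is lost.

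The size is illustrative and small. With one Day 84 escalator among 6, about 0.25 to 0.33 expected events sit in the other dose's column (18% to 22% of it), and the apparent rate ratio is 1.41 instead of 1.5, or 1.78 instead of 2. The SE of the log rate ratio is about 1.1. These figures rest on the assumed risk, rate ratios and switch time; only the group size and follow-up come from the documents. The case for a change is clear description of the primary endpoint at low cost, not correction of a distorted result.

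**What to change.** Keep the randomised-dose tables. Add to Part A SAP section 5.2.1:

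> If any subject changed dose in Part A, TEAEs, SAEs and AESIs will also be shown by actual daily dose at AE onset (each dose level received), with subject-time on each dose from the Study Drug Administration eCRF. With few switchers, a by-subject table of days and events on each dose may replace this. AEs whose onset date is too incomplete to place before or after the switch will be shown in a separate row and not assigned by the imputed date.

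The last sentence is needed because section 5.2.1 imputes partial onset dates to the first dose date, the first of the month or January, which would tend to place such events before the switch.

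In the AE listing, define treatment as dose at onset. In section 5.1.5, summarise exposure by actual dose as well. Label the added displays supplementary and non-randomised. Footnote three limits: switches follow safety and laboratory review; time after a switch is later study time; and events soon after a switch may reflect the earlier dose (Protocol section 5.2 reports a half-life of about 7.5 days in monkeys).

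The cost is a few conditional tables, or one short by-subject table, and one listing definition, from dosing data already listed. The risk is over-reading a confounded comparison, which the label and footnotes address. If the planned-output list already contains such a table, only the definitions and footnotes are needed.

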## Planned Dose Level

Planned doses through the Part A Core Study Phase (screening to Day 336) will be as follows:

	Cohort 1 wAIHA N= up to 12	Cohort 2 CAD N= up to 12
Group 1	Daily SC doses of 270 mg for 12 months (n= up to 6)	Daily SC doses of 270 mg for 12 months (n= up to 6)
Group 2	Daily SC doses of 360 mg for 12 months (n= up to 6)	Daily SC doses of 360 mg for 12 months (n= up to 6)

Following Month 12 and the completion of the Part A Core Study Phase, subjects will be eligible to participate in Part B, a Long-term Extension Phase, in order to continue to receive treatment with APL-2. During the Part A Core Study Phase this study will utilize an acetate buffered mannitol formulation of APL-2 (for the 270 mg/d and 360 mg/d doses). During the long-term extension phase, subjects will transition to APL-2 doses of 1,080 mg twice weekly, and may transition to 1,080 mg every three days (ie, a dose on every third day) if necessary.

Note: Some subjects may complete the Part A Core Study Phase prior to the availability of the acetate buffered sorbitol formulation. These subjects will continue with their 270 mg/d or

360 mg/d doses using the mannitol formulation until the acetate buffered sorbitol formulation is available.

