#### 15. STATISTICS

# 15.1 Sample Size Justification

As this is a pilot study the sample size is not based on formal statistical testing. The sample size is considered sufficient to obtain useful safety, tolerability, PD and PK data to assist the planning of future studies.

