## 4.3 Test Hypothesis and *P*-Value Justification

No formal inferential statistics will be applied to data collected in this study.

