## 4.5 Interim Analysis

One interim analysis is planned when all subjects enrolled in the study have completed Part A, the Core Study Phase (screening to day 336) or discontinued prior to Day 336. The interim analysis will present all planned tables, listings, and figures (TLF) listed in Appendix 8.1 for only the Part A Core Study Phase. The data will consist of:

- For subjects who rollover into the Part B Extension Phase, all data collected through the date of Visit 15 will be included. For occurrence data, such as Adverse Events and Concomitant Medications, records with a start date on or before the Visit 15 (which is considered the start of dosing date for the extension phase) will be included.
- For all subjects who do not rollover into the Part B extension Phase (i.e. who discontinue during the Part A Core Study Phase), all data will be included.

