## 5.2.1 Adverse Events

TEAEs are defined as those AEs that occur after Dosing on Day 1, or worsen in severity, and up to 30 days after the last dose of APL-2. For subjects who rollover to Part B long term extension phase, any AE recorded on the date of Visit 15 (start of dosing for the extension phase) will be included in Part A. Version 20.0 of MedDRA will be used to classify all AEs.

AEs will be considered treatment-emergent (TEAE) unless there is clear indication that the event occurred prior to first dose of study drug. AEs present prior to the first dose of study drug administration that increased in severity or relationship to study drug after the first dose of study drug and up to 30 days beyond the last dose of study drug will be classed as a TEAE. Events with missing or partial dates will be handled such that in the absence of contradictory information an AE is treatment emergent. So, for a missing start date (where stop date is after date of first dose) the date will be imputed as the date of first dose; for a missing stop date the date will be imputed as the last study date. If a partial date is recorded, the following convention will be used to assign the AE:

If a start date is missing the day information and month/year is the

same as first dose date then use first dose date, else '01' will be used for the day; if a start date is missing the month and the year is the same as first dose date then use first dose date, else January will be used for the start month.

• If a stop date is missing the day information and month/year is same as last study date then use last study date, else last day of the given month will be used for the stop day; if a stop date is missing the month and year is the same as last study date then use last study date, else December will be used for the stop month.

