# 5. STATISTICAL ANALYSIS METHODOLOGY

In general, tables will be presented by cohort (Cohort 1 wAIHA / Cohort 2 CAD) and study part (Part A + B / Part B). The Part B summaries will start from Study Day 1 in Part B through the end of the Part B Long Term Extension Phase, while Part A + B will start from Study Day 1 in Part A through the end of the Part B Long Term Extension Phase.

Tabulations for continuous data will use a standard set of descriptive statistics for the results and for change from baseline, as specified: number of observations available (n), mean, standard deviation (SD), median, and range (minimum, maximum). Change from Baseline for Part A + B summaries will calculate the Change from Part A Baseline summary statistics. Change from Baseline for Part B summaries will calculate the Change from Part B Baseline summary statistics.

Categorical or dichotomous data will be tabulated using frequencies (counts and percentages). The numerator and denominator for each percentage calculation will be specified in the footnotes of table shells. Categorical data will be populated as appropriate for each study part (Part A + B and Part B).

Data listings will present all information recorded in eCRFs for all subjects and visits. All listings will be sorted by cohort and subject number.

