#### Summary Tables by SOC and PT

The following tables will be presented with the number of events and the number/percent of subjects by cohort and by study part (Cohort 1 wAIHA Part B / Cohort 1 wAIHA Part A+ B / Cohort 2 CAD Part B / Cohort 2 CAD Part A + B).

- Non-ISR TEAEs by SOC and preferred term, including exposure-adjusted incidence
- TEAEs regarded as at least possibly related to study drug by SOC and preferred term, including exposure-adjusted incidence
- Injection Site Reaction TEAEs by SOC and preferred term, including exposure-adjusted incidence
- Serious AEs by SOC and preferred term, including exposureadjusted incidence

The summaries above will be ordered by alphabetical SOC and descending order of total event count of the term in Part A + B for the PT within each SOC.

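### Part A adverse event tables compare the randomised doses by crude counts and percentages, although time observed differs by subject status, and no AE table described in either SAP adjusts that comparison

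*SAP*

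**What the plan says.** The primary endpoint is the incidence and severity of TEAEs (Protocol 8.2; both SAPs 3.2.1). In the Part A SAP (27 Apr 2020), section 5.2.1, Adverse Events Summary, the main TEAE tables are to be "tabulated with the number of events and the number/percent of subjects by randomized dose level in each cohort". The severity and AESI tables give number and percent of subjects only.

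Two rules set how long each subject is observed. A TEAE must "occur after Dosing on Day 1, or worsen in severity, and up to 30 days after the last dose of APL-2" (Part A SAP 5.2.1). For the Part A report, section 4.5 adds: "For subjects who rollover into the Part B Extension Phase, all data collected through the date of Visit 15 will be included". Subjects who do not roll over contribute all their data, within the TEAE window.

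The Part B SAP (08 Nov 2022) defines exposure-adjusted incidence in 5.2.1.4. It uses it in 5.2.1.6, for example "Non-ISR TEAEs by SOC and preferred term, including exposure-adjusted incidence". Its general layout, in section 5, is: "In general, tables will be presented by cohort (Cohort 1 wAIHA / Cohort 2 CAD) and study part (Part A + B / Part B"). Its Safety Set (4.1) is limited to subjects who rolled over and received at least one 1080 mg dose.

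The Part A SAP also summarises, by randomised dose, exposure (5.1.5), early terminations with reasons (5.1.1) and TEAEs leading to drug discontinuation (5.2.1). The study is descriptive: "No formal inferential statistics will be applied to data collected in this study" (both SAPs, 4.3).

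**The concern.** A count or percentage of subjects with an event depends on the event rate and on how long subjects were watched. If the two dose groups differ in early stopping or in the share rolling over, their crude figures can differ with no difference in event rate, or agree when the rates differ.

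The Part A report is the only planned analysis that sets harms side by side by randomised dose. The later analysis, which does divide by time at risk, drops the dose split and excludes anyone who stopped before receiving 1080 mg. Protocol 7.2.1 says that including two doses is meant to help identify an optimal dose, so the harms comparison bears on a stated purpose of the design. With at most six subjects per dose and cohort, one or two early stops change a group's total follow-up noticeably.

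**Working it through.** **The plan's own figures.** There is no power or event-rate figure to reproduce: "As this is a pilot study the sample size is not based on formal statistical testing" (Protocol 15.1). The group size is up to six; the Protocol synopsis dose table has "Daily SC doses of 270 mg for 12 months (n= up to 6") and the same number for 360 mg. Two cohorts × two doses × 6 = 24, which matches the planned maximum.

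**Observation windows at target visit days**
- Rollover: to Visit 15, 336 days.
- Completer without rollover: 336 + 30 = 366 days (366/336 = 1.089, or 9% longer).
- Stopper at day T: T + 30 days. This equals the rollover window at T = 336 − 30 = 306.

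**Loss of person-time.** Compare a group of six with k stoppers at day T, the rest rolling over, against six rollovers (6 × 336 = 2016 person-days). Person-days = (6 − k) × 336 + k × (T + 30). For an event with 50% risk by Day 336 and constant hazard h = ln 2/336, with stopping unrelated to the event, expected percent = [(6 − k) × 0.5 + k × (1 − exp(−h(T + 30)))]/6. The hazard and the stop patterns are assumptions.

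| Stops | Person-days | Change | Expected % (50% if none stop) | Rate ratio hidden by equal event counts |
|---|---|---|---|---|
| 1 at Day 28 | 5 × 336 + 58 = 1738 | −14% | 43.5 | 2016/1738 = 1.16 |
| 2 at Day 84 | 4 × 336 + 2 × 114 = 1572 | −22% | 40.3 | 2016/1572 = 1.28 |
| 3 at Day 56 | 3 × 336 + 3 × 86 = 1266 | −37% | 33.1 | 2016/1266 = 1.59 |

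With person-time as the denominator, the expected rate ratio is 1.00 in every one of these equal-hazard cases.

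**Does the direction hold?** Take two stops at Day 84 and three assumed event rates λ per person-year. Let p = 1 − exp(−λ × 336/365.25). If the stops are unrelated to events, the stoppers' risk runs over 114 days. If an adverse event causes each stop, both stoppers count as having an event, and the expected percent is (2 + 4p)/6.

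| λ | No stops, % | Two unrelated stops, % | Two AE-driven stops, % |
|---|---|---|---|
| 0.5 | 36.9 | 29.4 | 57.9 |
| 1 | 60.1 | 49.0 | 73.4 |
| 2 | 84.1 | 71.6 | 89.4 |

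The sign depends on why subjects stop. Event counts need not move with percentages. With AE-driven stops, counting only the two stopping events, the stoppers' 30-day tails and the four rollovers, the expected count is at least 4λ × 336/365.25 + 2 + 2λ × 30/365.25. That gives 3.9, 5.8 and 9.7, against 2.8, 5.5 and 11.0 with no stops.

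Late stopping does not shorten follow-up: two of six stopping at Day 320 gives (4 × 336 + 2 × 350)/2016 = 1.014.

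**Precision after adjustment.** Six rollovers give 2016/365.25 = 5.52 person-years. Six events are 108.7 per 100 person-years (exact 95% CI 39.9 to 236.6); three events are 54.4 (11.2 to 158.8).

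**The case against.** A reader might infer that the dose group with more early stoppers will always look safer. The documents do not support that. They give no stopping rate or reason mix, and the working shows that stops caused by adverse events raise the crude percentage. Poor tolerability is a likely reason for stopping, so this is not a remote case.

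A reader might also infer that the Part A report contains no information on time. That is not so. Exposure, early terminations with reasons and TEAEs leading to discontinuation are all summarised by dose, and the AE listing carries start day and duration. In cells of six, unequal stopping would be visible and a rough overall event rate could be worked out. These outputs do not, however, give rates by preferred term, time to first event, or denominators that follow the status-specific windows.

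Other points against have some weight:
- The shifts from 50% to 43.5%, 40.3% and 33.1% amount to 0.4, 0.6 and 1.0 subject out of six, well inside the interval for any adjusted rate.
- The sponsor may replace withdrawn subjects (Protocol 12.8).
- Rollovers remain on drug at Visit 15, so they have no off-drug period at that visit to lose.
- Doses may change during Part A (Protocol 9 and 11.3.4; Part A SAP 3.3), so person-time by randomised dose may mix both doses.
- Rates assume a roughly constant hazard. If events cluster early, they can overstate the rate in the group with stoppers.

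These limit how much weight an adjusted figure can carry. They do not make the crude figure a clean comparison, because it is just as small-sample and also carries the follow-up difference.

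**Conclusion.** The point holds in a limited form. In every AE table that the text of the two SAPs describes, the comparison of harms between randomised doses is unadjusted for time observed, while the SAP's own rules give subjects unequal time. The list of planned outputs in the Part A SAP appendix was not available for this review, so the statement goes no further than the text.

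In the patterns worked through, person-time falls by 14% to 37% in a group of six, and equal event counts would hide a rate ratio of 1.16 to 1.59. These sizes rest on assumed stop days, and the expected percentages also on a constant hazard and stopping unrelated to the counted event. The direction of any distortion is not fixed. A group with more stops can look safer when stopping is before about Day 306 and unrelated to the events counted; it can look worse when events cause the stops.

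This is a worthwhile, inexpensive improvement to a descriptive safety report. It does not invalidate the planned tables.

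**What to change.** In Part A SAP 5.2.1, or in a labelled supplementary Part A table because SAP version 1.0 has already been used for the interim analysis, add person-years and exposure-adjusted incidence by randomised dose within cohort. Apply this to the TEAE, related TEAE, serious TEAE and AESI summaries; injection-site reactions fall under AESI.

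- Use the formula in Part B SAP 5.2.1.4, with time ending at the first event. For subjects without the event, end time at the earliest of Visit 15 (rollovers), last dose + 30 days, death or last contact. The Part B formula censors at last dose + 56 days, so that term must change to match the Part A TEAE window.
- State the numerator. Part B SAP 5.2.1.4 describes it in words as events but defines n as subjects with an event.
- Keep the crude counts and percentages beside the rates.
- Footnote that person-time by randomised dose includes time after any dose switch.

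The cost is SAP wording and extra columns, from dosing dates, AE start dates and Visit 15 dates already collected. The downside is imprecise rates in cells of up to six that lean on a roughly constant hazard, which is why the crude columns stay.
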